Until now, researchers consider that the aetiology of type 2 diabetes mellitus is unknown. There are several hypotheses that try to explain the origin of the disease, such as that it is a disorder of the anterior hypothalamus and the endocrine pancreas caused by progressive ischemia or that there is an abnormal innervation of the islets. Recently, the study of the innate immune system has thrown some light, as there is increasing evidence of an inflammatory acute phase response induced by cytokines, closely linked with the generation of insulin resistance and diabetes. Other studies have associated these pathologies with the presence of inflammatory and immune biomarkers such as TNF- α , IL-1, IL-6, C Reactive Protein (PCR), Monocyte Chemotactic Protein-1 (MCP-1), sialic acid, leptin, adiponectin, resistin and visfatin.

Next to inflammation, patients with diabetes face greater risk of certain infections, including influenza, pneumonia, and foot infections. These infections are associated with increased morbidity and mortality.

Dysbiosis of gut microbiota has also been associated to insulin resistance and low-grade chronic inflammation in the development of type 2 diabetes mellitus.

There is evidence suggesting that supplementation with vitamin C, vitamin D or zinc may help patients with type 2 diabetes mellitus achieve a better metabolic control, thus aiding in the prevention of complications at various levels.

Hypothesis:

1. Vitamin C, vitamin D and zinc supplementation decreases pro inflammatory cytokines (TNF α , IFN- γ , IL-1 β) and improves anti-inflammatory (IL4, IL-6, IL10, TGF- β) in patients with type 2 diabetes mellitus.
2. Type 2 diabetes mellitus patients supplemented with vitamin C, vitamin D and zinc will have a better metabolic control.
3. Microbiota of patients with Type 2 diabetes mellitus will have a better profile after supplementation with vitamin C, vitamin D and zinc.
4. Vitamin C, vitamin D and zinc supplementation decreases oxidative stress levels (MDA and protein carbonyl) and improves antioxidant systems

(antioxidant capacity, enzymatic activity: catalase, superoxide dismutase and glutathione peroxidase) in patients with type 2 diabetes mellitus.

3. Objectives

General objective:

To evaluate the effect of vitamin C, vitamin D and zinc supplementation on glucose metabolism, inflammatory and immune system biomarkers, oxidative stress and gut microbiota in patients with type 2 diabetes mellitus in the State of Mexico.

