Specific objectives:

1. To evaluate the effect of vitamin C, vitamin D and zinc supplementation on metabolic control (plasma glucose, HOMA, Hb1Ac and lipid profile).
2. To analyse the effect of vitamin C, vitamin D and zinc supplementation on inflammatory and immune biomarkers.
3. To analyse the effect of vitamin C, vitamin D and zinc supplementation on oxidative stress and antioxidant profile.
4. To evaluate the effect of vitamin C, vitamin D and zinc supplementation on gut microbiota.

4. Methods

Study design

Clinical trial randomized, prospective, placebo-controlled, double blinded, comparing two groups of patients with type 2 diabetes mellitus in the State of Mexico.

According to the calculation of the sample size, we will include 120 adults with type 2 diabetes mellitus selected from the outpatient preventive medicine offices of health centres in the State of Mexico who will be divided in two groups: supplement and placebo (60 per group). After having been invited to participate and obtaining the informed consent, study subjects will be evaluated for dietary information, as well as biochemical biomarkers of metabolic control, anthropometric, immune and inflammatory markers, gut microbiota and oxidative stress, before beginning the trial, and after 12 and 24 weeks of supplementation. They will have a monthly follow-up visit for evaluation of adherence and adverse effects, as well as delivery of the supplement.

Study groups

Subjects will be randomly allocated to a supplementation with 1000 mg vitamin C, 400 IU vitamin D and 10 mg of zinc or placebo group, during 24 weeks. Subjects and researchers will be blinded to the supplement or placebo in order to guarantee double-blinding.

Sample size calculations:

Based on a previous study done by this same research group (*Nutrients* 2017, 9, 573; doi:10.3390/nu9060573), we calculated the sample size with the data on the effect of a

6-month *n*-3 fatty acid supplementation trial on glucose concentrations of group of subjects with type 2 diabetes mellitus,

The calculations were done with the following formula:

$$N = \frac{(2 \times s^2)(Z\alpha + Z\beta)^2}{d^2}$$

Where: $Z_{\alpha/2} = 1.96$, $Z_{\beta} = 0.84$, $s = 68.9$ mg/dL and $d = 40$ mg/dL

Thus:

$$N = \frac{(2 \times 4747.21)(1.96 + 0.84)^2}{40^2} = 46 \approx 50 \text{ subjects}$$

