A qualified physician will do a complete clinical history. Subjects will be requested to fill-out the Diabetes 39 quality of life questionnaire (validated in Mexico), at baseline and at the end of the study. Questions on frequency of respiratory, urinary and gastrointestinal infections as well as on perception with respect to the supplement will be included.

A standardized nutritionist will evaluate Dietary History, a food-frequency questionnaire (FFQ), as well as three 24-hour food registry of non-consecutive days including one from the weekend. The FFQ will be analysed in DIAL software to evaluate dietary intake of vitamin C, vitamin D and zinc. Anthropometric evaluations will be done by a standardized nutritionist; weight will be measured with a 1631 TANITA™ portable electronic scale, stature with a 1013522 SECA™ portable stadiometer, for the calculation of BMI.

Faecal samples will be obtained for evaluation of intestinal microbiota. We will proceed to isolate and characterize the bacteria obtained from the faecal samples with two enriched culture media for the purification of the most representative and abundant strains. The isolated strains will be classified in morphological groups according to their macroscopic characteristics of size, form, surface, consistency and color. A selection of 40% of the representative samples from each morphologic group will be typified by the RFLP method. We will obtain biomass and extract DNA, for amplification of the 16S rRNA gene, with an enzymatic genotyping and strain grouping. The strains will be grouped to compare their diversity; the results of the groups will be compared to appreciate the differences between the type and number of strains obtained.

At each sampling date, a venous blood sample of 8.5 mL will be obtained after a 12 hour fast for the measurement of vitamin C (HPLC); zinc (Atomic Absorption Spectrometry); vitamin D and Vitamin D binding protein (ELISA); plasma glucose; triacylglycerides; total cholesterol; HDL and LDL-cholesterol and Hb1Ac (Automated Selectra equipment with Randox™ reactants); pro inflammatory cytokines (TNF α , IFN- γ , IL-1 β) and anti-inflammatory cytokines (IL4, IL-6, IL10, TGF- β), apolipoproteins A and B, C-reactive protein, V-CAM, I-CAM, complement proteins C-3 and C-4, insulin, adiponectin, resistin and leptin will be analysed with multiplex technology (Milliplex Luminex™). Additionally we will measure biomarkers of oxidative stress and

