A specific database will be designed in SPSS 19.0®. Data will be described with means and standard deviations or frequencies and percentages depending on the type of data. We will undertake a normality analysis, after which differences between groups will be analysed by parametric or non-parametric statistical tests. A multiple regression analysis will be run in order to establish interactions between variables.

References

Barengolts E. Vitamin D and prebiotics may benefit the intestinal microbacteria and improve glucose homeostasis in prediabetes and type 2 diabetes. *Endocr Pract* 2013; **19**(3): 497-510. doi: 10.4158/EP12263.RA.

Crook M. Type 2 diabetes mellitus: a disease of the innate immune system? An update. *Diabetic Medicine*. 2003; **21**:203-7.

Diabetes Public Health. From Data to Policy: Oxford University Press; 2011

Encuesta Nacional de Salud y Nutrición 2012. http://www.insp.mx/ensanut/resultados_ensanut.html.

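### Typing a fixed 40% of isolates and comparing raw strain counts makes the microbiota result depend on culture yield, and no common typing depth or per-participant diversity value is set

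*Combined protocol and SAP*

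**What the plan says.** The laboratory plan is in section 4 (Methods), under Measurements. Faecal bacteria are isolated "with two enriched culture media for the purification of the most representative and abundant strains" and sorted by colony appearance. Then "A selection of 40% of the representative samples from each morphologic group will be typified by the RFLP method". On the comparison, the text says "The strains will be grouped to compare their diversity", and that "the results of the groups will be compared to appreciate the differences between the type and number of strains obtained".

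The section gives no number of colonies to pick per stool sample, no fixed number to type, no rule for choosing the 40%, no diversity index, and no summary per participant and visit. Samples are taken at baseline, 12 weeks and 24 weeks.

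The only analysis text is under Data Collection and Statistical Analysis: "differences between groups will be analysed by parametric or non-parametric statistical tests", followed by a multiple regression. It does not mention microbiota, the unit of analysis, or several isolates and three visits per person.

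Hypothesis 3 (section 2) is that "Microbiota of patients with Type 2 diabetes mellitus will have a better profile after supplementation", and specific objective 4 (section 3) rests on the same data. The randomised unit is the subject, and subjects and researchers are blinded (Study groups).

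**The concern.** A count of distinct types is not comparable between samples typed to different depths: the more isolates are typed, the more types appear. A proportional rule passes any difference in recovery straight into the outcome. Recovery could differ by arm or visit through stool handling, through culture conditions over time, or because the supplement changes what grows on the two media. The trial could then report more or less diversity when only the number of recoverable isolates had changed.

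The second issue is the unit. The text speaks of grouping strains and comparing the results of groups, and these could be trial arms or strain groups. If isolates were pooled by arm and tested as independent, correlation within a person would be ignored, and the richness of the pool would also depend on how many participants remained in it.

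**Working it through.** **The plan's own figures.** None exists for microbiota. The only sizing calculation is for glucose: 2 × 68.9² × (1.96 + 0.84)² / 40² = 46.5 per group, against 46 stated. It does not bear on this point. From the plan come the 40% fraction, 60 per group and 20% loss (60 × 0.8 = 48 analysed). Every other input below is an assumption.

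**1. Typing depth and number of types.** With S equally abundant types and k isolates typed, the expected number of distinct types is S × [1 − (1 − 1/S)^k]. Take S = 40, with k equal to 40% of the isolates:

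| Isolates | Typed (k) | Types, equal abundance | Types, lognormal abundance (log SD 1) |
|---|---|---|---|
| 20 | 8 | 7.3 | 6.7 |
| 25 | 10 | 8.9 | 8.0 |
| 30 | 12 | 10.5 | 9.3 |
| 50 | 20 | 15.9 | 13.4 |

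Going from 10 to 20 typed raises the count by 15.89/8.95 − 1 = 78% (equal abundance) or 13.41/8.03 − 1 = 67% (lognormal). Going from 10 to 12 raises it by 10.48/8.95 − 1 = 17%. The community is the same throughout. Typing 8 every time gives 7.3 or 6.7 whatever the yield.

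**2. Participant as unit.** Simulated two-arm t-tests of one type count per participant used identical communities, 40 lognormal types, 48 per arm, a 20% coefficient of variation in isolates, and 1,000 trials:

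| Mean isolates by arm | Significant at 5%, 40% typed | Significant at 5%, 8 typed each |
|---|---|---|
| 30 v 30 | 5% | 5% |
| 30 v 31.5 | 16% | 5% |
| 30 v 33 | 37% | 5% |
| 30 v 36 | 88% | 4% |

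A second run of the three unequal scenarios gave about 13%, 33% and 89% under 40% typing.

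**3. Isolates pooled and treated as independent.** With k typed per person, the design effect is DE = 1 + (k − 1) × ICC, and the actual error of a nominal 5% test is 2 × [1 − Φ(1.96/√DE)]. For k = 10:
- ICC 0.1: DE 1.9, error 16%
- ICC 0.3: DE 3.7, error 31%
- ICC 0.5: DE 5.5, error 40%

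This applies to isolate-level means or proportions, such as the share of isolates of a given type. It does not apply to a count of distinct types.

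**4. Pooled richness and retention.** With 12 typed per person and 300 lognormal types (log SD 1.5), pools from 60 and 48 participants contain about 166 and 153 types from the same community.

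**The case against.** The plan is incomplete here rather than plainly wrong, and much of this objection stands.

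- A reader might infer that every interpretation of the word groups leads to a faulty comparison. The documents do not support that. Subjects are randomised, and the general analysis text can be read as one type count per subject compared between arms. With equal mean yield, that test holds its 5% level.
- A reader might infer that the expected 20% loss creates a false difference between arms. The allowance is the same in both groups and nothing predicts unequal loss. With participant-level counts and equal mean yield, simulated error was 4.7% with 60 v 48 retained and 4.6% with 54 v 42. Retention distorts only pooled richness, and the plan does not clearly prescribe pooling.
- The 40% applies to representative samples within each morphologic group, which is not plainly all isolates. If a fixed number of colonies were picked per sample, 40% of it would also be fixed. The plan does not fix that number.
- "Subjects and researchers will be blinded to the supplement or placebo in order to guarantee double-blinding". Blinding limits deliberate unequal effort, but it cannot equalise culturable yield if the supplement alters it.
- The number of strains obtained is part of the stated comparison, so a change in yield may be a real effect. That is a reason to report it, separately from diversity.

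What remains is that a raw count under a proportional rule cannot separate yield from diversity, and nothing in the analysis text corrects this.

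**Conclusion.** The concern holds in conditional form. The count of distinct types depends on how many isolates were recovered, so a difference in culturable yield by arm or visit would be read as a difference in diversity. If yield is equal on average and each participant contributes one value, the error stays near 5%. If isolates were pooled by arm as independent observations, the error would be inflated; the plan neither prescribes nor excludes this.

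The documents do not show that bias will occur, and they give no basis for its size. The figure of 40 types is an assumption. The Gut microbiota background says that about 40 species make up 75% of abundance, which is not a count of RFLP types culturable on two media. Equal or lognormal abundance, isolates per person, ICCs and yield differences are assumed as well. The 78% needs a doubling of typed isolates, which nothing in the plan suggests.

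Microbiota is one of four specific objectives and the sample size rests on glucose. The change is therefore an inexpensive improvement to one objective, and it does not put the trial as a whole in question.

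**What to change.** Before any samples are processed:

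1. Set an equal number of isolates to type per participant and visit, or rarefy to a common number.
2. Select the isolates to type at random, under coded identifiers.
3. Report isolate yield per sample as its own result, separate from diversity.
4. Compute one richness or Shannon value per participant and visit.
5. Compare arms on the 24-week value, with the participant as the unit and the baseline value as covariate.
6. Word the conclusions for specific objective 4 and Hypothesis 3 as applying to cultivable faecal bacteria, since only two culture media are used.

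**Cost.** This is wording in the laboratory procedure and the analysis plan, using samples already scheduled. The total typing load can stay the same. Rarefying discards some typed isolates, and the microbiota claim becomes narrower. The typing number needs to be set early, because isolates that were never typed may not be recoverable later.

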There is not much information on the effect of zinc or vitamin C supplementation on gut microbiota. However, Vitamin D may promote a reduction in opportunistic pathogens and an increase in bacterial diversity in the gut. Vitamin D and its receptor (VDR) help in controlling dysbiosis, maintaining gut tolerance and protecting from chronic gastrointestinal diseases, through regulating microbiota composition and function in the intestine.

Oxidative stress

There is evidence that oxidative stress, defined as a persistent imbalance between the production of highly reactive molecular species (chiefly oxygen and nitrogen) and antioxidant defenses, leads to tissue damage. Oxidative stress results from increased content of reactive oxygen species (ROS) for example: superoxide and the hydroxyl radical, and uncharged species such as hydrogen peroxide. There are data indicating that ROS formation is a direct consequence of hyperglycemia; more recent studies have suggested that increased free fatty acid levels may also result in ROS formation. Because of their ability to directly oxidize and damage DNA, protein, and lipid, ROS are believed to play a key direct role in the pathogenesis of late diabetic complications.

Previous experimental and clinical studies report that oxidative stress plays a major role in the pathogenesis and development of complications of diabetes mellitus. However, the exact mechanism by which oxidative stress could contribute to and accelerate the development of complications in diabetic mellitus is only partly known and remains to be clarified. Hyperglycemia induces free radical production; on the other hand, it impairs the endogenous antioxidant defense system in patients with diabetes. Endogenous antioxidant defense mechanisms include both enzymatic and non-enzymatic pathways. Their functions in human cells are to counterbalance toxic reactive oxygen species (ROS). Common antioxidants include the vitamins A, C, and E, glutathione (GSH), and the enzymes superoxide dismutase (SOD), catalase (CAT), glutathione peroxidase (GPx), and glutathione reductase (GRx).

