In diabetes, oxidative stress is caused by increased formation of plasma-free radicals and a reduction in antioxidant defenses. Hyperinsulinemia and hyperglycemia may enhance the production of free radicals and induce oxidative stress. There is considerable evidence that oxidative stress plays a key role in insulin resistance, impaired insulin secretion, and many of the complications of diabetes such as micro-/macro-vascular damage. SOD and GPx are antioxidant enzymes that protect the body against active oxygen-free radicals. Some experimental studies showed that Vitamin D may have antioxidant properties by modifying some of the antioxidant enzymes.

2. Problem

Chronic diseases have become one of the most important public health problems in the world, due to the high costs of treatment and control of complications. Changes in human behaviour and lifestyles in the last century have caused an increase in type 2 diabetes mellitus.

Chronic elevation of blood glucose, even in absence of symptoms, causes damage in several tissues, particularly microcirculation in the retina, kidneys and peripheral

nerves, where the diabetic complications are more evident. This has led to an increase in the incidence of blindness, amputations and renal failure in many countries, developed and developing. Individuals with diabetes have a two to four-fold higher risk than the general population of developing cardiovascular disease; between 50 and 80% of patients with diabetes die of heart disease or its complications, which also favour the development of disabilities, decrease in life expectancy and the use of a large amount of the health services' budget.

In Mexico, the situation of the health service system is complex, as there is a co-existence of chronic and infectious diseases. Type 2 Diabetes Mellitus was prevalent in 8 to 9% of the Mexican population and it is estimated to increase to 12.3% by the year 2025. Since 1940, diabetes has been in the list of the first 20 main causes of mortality, but since 2000, it is the first cause of death in women and the second in men (after ischemia). In 2003, diabetes caused 12.6% of all deaths in the Mexican population, with a mean age of death of 66 years. However, the National Nutrition Survey of 2012 (ENSANUT 2012) indicated that 9.2% of Mexican adults have been diagnosed with diabetes. It is also the main cause of medical outpatient attention and hospitalization.

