antioxidant systems such as Malondialdehyde (QuantiChrom™ TBARS Assay Kit), protein carbonyls (calorimetric assay), antioxidant capacity (QuantiChrom™ Antioxidant Assay Kit), Catalase activity (EnzyChrom™ Catalase Assay Kit), Superoxide Dismutase activity (EnzyChrom™ Superoxido Dismutase Assay Kit) and Glutathione Peroxidase (metaphosphoric acid SIGMA ALDRICH and EnzyChrom™ GSH/GSSG Assay Kit).

HOMA-IR and HOMA-B

HOMA_{IR} will be calculated as follows: HOMA_{IR} = (insulin x glucose)/405

HOMA-B will be calculated as follows: HOMA-B = 20 × insulin (μUI/mL) / (glucose [mmol/L] – 3,5) (160).

Follow-up

Additionally to their monthly visits to the clinic, the researchers will maintain close communication via telephone or e-mail with all participants, to promote adherence, and to identify any possible adverse effect of the supplements. Adherence will be evaluated by the Morisky-Green and Haynes-Sackett tests.

The investigators will collect, document, report and follow-up all events that meet the definition of an adverse event (AE) or serious adverse event (SAE) to the Health Authority (COFEPRIS) or the Ethics Committee in accordance with local legal obligations. AEs/SAEs will be collected from the first day the subject consumes the supplement up to three months after end of supplementation.

Adverse effects will also be registered during the monthly follow-up visits. If an adverse effect that puts the subject at risk is identified, such as an allergy, the supplementation will be suspended and reported to the authorities (COFEPRIS), as well as the producers of the supplement.

Bioethics

This project will be conducted according to the Declaration of Helsinki and all its amendments, including the one in 2013. We will also abide by the General Health Law of the Mexican Ministry of Health with respect to research in human beings.

The protocol will be reviewed and approved by the Research and Ethics Committees of the Faculty of Medicine of the Universidad Autónoma del Estado de México.

Participation in the study will be totally free and voluntary, subject to the participants' authorization by the signature of a letter of informed consent.

The procedures in the present study are considered with a risk higher than minimum, due to the need to draw blood by venipuncture.

All information will be maintained confidential.

Data Collection and Statistical Analysis

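### Hypothesis 4 predicts glutathione peroxidase activity, but the only method named for it is a GSH/GSSG kit; outcome and method must be reconciled before samples are assayed.

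*Combined protocol and SAP*

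**What the plan says.** All references are to the combined protocol and SAP.

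- **Section 2, Hypothesis, item 4.** Supplementation is predicted to improve the antioxidant systems, spelled out as "antioxidant capacity, enzymatic activity: catalase, superoxide dismutase and glutathione peroxidase".
- **Section 4, Measurements.** The entry for this marker reads "Glutathione Peroxidase (metaphosphoric acid SIGMA ALDRICH and EnzyChrom™ GSH/GSSG Assay Kit".
- **Background, Oxidative stress.** The text separates two kinds of defence: "Endogenous antioxidant defense mechanisms include both enzymatic and non-enzymatic pathways". Its list of common antioxidants then runs on to "glutathione (GSH), and the enzymes superoxide dismutase (SOD), catalase (CAT), glutathione peroxidase (GPx), and glutathione reductase (GRx", so glutathione and the peroxidase are distinct items. Later it adds that "SOD and GPx are antioxidant enzymes that protect the body against active oxygen-free radicals".
- **Section 3, Specific objectives, item 3.** The objective is "To analyse the effect of vitamin C, vitamin D and zinc supplementation on oxidative stress and antioxidant profile". It names no individual marker.
- **Section 4, Study design.** Assessments include "gut microbiota and oxidative stress, before beginning the trial, and after 12 and 24 weeks of supplementation".

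**The concern.** The outcome is named as an enzyme and predicted as an enzyme activity, but the method attached to it is named for a different molecule. If the laboratory follows the entry as it stands, the group comparison under the enzyme's name will be a comparison of glutathione. Neither a difference nor its absence would then bear on what hypothesis 4 predicts for glutathione peroxidase. The same mislabelled variable would also enter the antioxidant profile that specific objective 3 sets out to analyse.

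**Working it through.** The plan gives no figure specific to this marker, so the check is mainly a comparison of text. A count of affected results follows.

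**1. The three enzymes of hypothesis 4 against the assay list in Measurements**

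| Enzyme | Labelled as an activity? | Kit named for that enzyme? |
|---|---|---|
| Catalase | yes | yes |
| Superoxide dismutase | yes | yes |
| Glutathione peroxidase | no | no: metaphosphoric acid and a GSH/GSSG kit |

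Two of the three enzyme predictions have a matching assay and the third does not.

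**2. What the abbreviations mean.** The Oxidative stress background expands GSH as glutathione and GPx as the peroxidase, and places only the latter among the enzymes. By the protocol's own terms, the kit name points to glutathione and the outcome label to the enzyme. The document does not expand GSSG, describe the kit or say what the acid is for. The reading that the kit quantifies reduced and oxidised glutathione, and that neither item is an activity assay, therefore rests on the kit's name and general laboratory usage.

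**3. Does anything else resolve it?** No other section names a glutathione peroxidase assay or explains how activity would be derived from GSH/GSSG. None lists glutathione as a planned measurement in its own right.

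**4. Which side is the slip?** The evidence points both ways.
- For the enzyme: the label on the entry itself, the wording of hypothesis 4, and the rationale in the background that "Some experimental studies showed that Vitamin D may have antioxidant properties by modifying some of the antioxidant enzymes".
- For glutathione: the entry gives two specific items, the acid with its supplier and the kit, and neither names the enzyme. The vitamin C background also cites a rise in glutathione levels after supplementation with vitamins C and E.

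**5. Number of results concerned.** Inputs: 120 participants, 60 per group, and three sampling dates (Study design); 10 added per group for losses, 50 + 10 = 60 (Sample size calculations). I assume one result per participant per date, because replicates are not stated.
- No losses: 120 × 3 = 360.
- All planned losses before week 12: 60 − 10 = 50 per group, or 100 in total, at weeks 12 and 24; 120 + 100 + 100 = 320.
- If the kit name is the slip: 0 mislabelled results.

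**6. Reach.** Measurements names six oxidative-stress and antioxidant markers: malondialdehyde, protein carbonyls, antioxidant capacity and the three enzymes. This is one of the six. The sample-size formula takes only glucose inputs (s = 68.9 mg/dL, d = 40 mg/dL), so nothing in it depends on this marker.

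**The case against.** The strongest reply is that this may be no more than a miscited kit. If the laboratory intends and runs a peroxidase activity assay, no result is mislabelled and the error is confined to one line of an assay list. That stands as a possibility, and the document does not exclude it. It does not remove the need for correction, because the opposite reading is equally open and a reader cannot tell which to apply.

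A second reply is that the document never says what the kit measures. This also stands, as a limit on the evidence. The mismatch between the outcome label and the kit name is in the text; what the kit can and cannot measure comes partly from outside it. A derivation of activity from GSH/GSSG may have been intended, but none is stated.

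A third is that the list of oxidative-stress markers is introduced as examples, so an unlisted assay could exist. That does not help, because this entry is explicitly the method given for glutathione peroxidase.

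Finally, only one marker is involved and the sample size rests on glucose. That is correct and limits the weight of the point.

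**Conclusion.** The plan is internally inconsistent and wrong as written: hypothesis 4 and the Measurements entry do not describe the same quantity. Followed literally, the entry would put 320 to 360 glutathione results under the enzyme's name. They could not support a conclusion, for or against, on one of the three enzyme predictions in hypothesis 4, and they would enter the antioxidant profile of specific objective 3 mislabelled. If the kit name is the slip, the consequence is a correction to the assay list.

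This rests on the reading of the kit from its name and usage, and on one result per participant per date. The counts show how many results are concerned, not how large any bias is; the document gives no data from which an effect on a treatment estimate could be computed.

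A reader might infer that the trial will certainly fail to measure glutathione peroxidase, or that the whole of hypothesis 4 or objective 3 is lost. The document supports neither inference. It leaves open which side is the slip, and the other five named markers are not touched by this point.

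**What to change.** Before samples are assayed, the laboratory should confirm which measure is intended, including whether any derivation of enzyme activity from GSH/GSSG was meant. Hypothesis 4 and the Measurements entry should then be reconciled in one of two ways.

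- **(a) The enzyme is intended.** Replace the whole entry with a named glutathione peroxidase activity assay and keep hypothesis 4. This covers the kit, and the metaphosphoric acid step if it does not belong with the new assay. Cost: one assay substituted, at a price the document does not give.
- **(b) Glutathione is intended.** Keep the method and rename the outcome glutathione (GSH/GSSG). State before analysis whether GSH, GSSG or their ratio is compared, and remove glutathione peroxidase from the conclusions under hypothesis 4. Cost: nothing changes in the laboratory, but one of the three enzyme predictions is given up.

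Timing matters because the document does not mention stored samples. If none are kept, option (a) may no longer be available once the samples have been used; the laboratory should confirm this too.
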